17.5 Appendix E: SOP for Transduction

17.6 Appendix F: Monitoring for monoclonal expansion or leukoproliferation due to insertional oncogenesis

A general protocol for investigation of possible clonal proliferations that might develop as a result of insertional oncogenesis will be followed. The purposes of the protocol are to:

Provide adequate monitoring so that determination of the need for therapeutic intervention is made as expeditiously as possible;

Minimize the risk of either physical or psychological harm of unnecessary interventions, to which subjects are exposed;

Characterize any clonal proliferation events occurring in gene therapy trials;

Determine whether any clonal proliferation resulted from insertional oncogenesis;

Characterize the clonality of the normal, genetically-modified hematopoiesis after γ -retroviral gene therapy of HSC.

[figure not shown]
Clonal Monitoring Methods

The methods used to characterize clonal expansion in the gene therapy trials for X-SCID included LAM-PCR and TCR spectratyping. LAM-PCR (linear amplification mediated PCR) is based upon isolation of genomic DNA from peripheral blood mononuclear cells, primer extension with a 5' biotinylated primer, avidin bead isolation of the products, restriction digest to cut a 3' site, then PCR methods to amplify the antisense strand using a linker-based 3' primer. Each unique resulting band represents an individual integration site. The sequence can then be identified by searches against the human genome to determine the proviral integration site.

Information about clonality can also be gained from analyses of immunoreceptor gene rearrangements, for example, spectratyping of the TCR for T cells, and by an analogous approach for the B cell receptor (BCR) expressed by B lymphocytes. Since the TCR and Ig immunoreceptor genes are the only known genes to normally undergo rearrangement in lymphohematopoietic development, analyses of hematopoietic clonality can only be applied to the study of T and B lymphocytes, thus precluding monitoring of NK cells or non-lymphoid cells, such as myeloid cells. Furthermore, clonal lymphocyte proliferation with certain immunoreceptor rearrangements or with multiclonal rearrangements may not be detectable.

Insertional oncogenesis following gene transfer into hematopoietic stem cells could theoretically result in either lymphoid or myeloid leukemias. The techniques used to characterize the T cell lymphoproliferation occurring in X-SCID patients after gene therapy may not be adequate for other forms of malignant expansion, and it is important that monitoring protocols are identified that can be applied to all patients and possible different outcomes.

MONITORING PROPOSAL: GENE TRANSFER TO CD34+ HEMATOPOIETIC STEM CELLS

¹ A approximately every 6 months for the first 5 years on study, then annually for the next 10 years. (If at 2 years, marking is low or absent, and / or monoclonality is stable, the plan may be modified with regulatory agency guidance). CBC = complete blood count with differential; LAM-PCR = ligation/amplification mediated polymerase chain reaction; PBMC = peripheral blood mononuclear cells; S.D. = standard deviation; TCR = T cell receptor; EBV = Epstein-Barr virus; BCR = B lymphocyte receptor; BM = bone marrow.

Protocol for monitoring and evaluation of increasing oligoclonality or monoclonality:

In order to monitor subjects for evidence of uncontrolled leukocyte proliferation, the following protocol will be used:

1. Clinical Assessment

Clinical evaluation for evidence of leukocyte proliferation, or cytopenia - Physical evaluation and imaging studies (as indicated) for evidence of lymphadenopathy, hepatomegaly, splenomegaly.

2. Screening Laboratory Assessment

CBC with differential to determine whether there is evidence of leukocytosis, or cytopenia. Leukocytosis will be defined as values that are $> 15,000 / \text{mm}^3$ on two successive analyses, within a clinically-appropriate time-frame and in the absence of signs of infection. Cytopenia will be defined as platelets $< 100,000/\text{ul}$, leukocytes $< 1,500/\text{ul}$, or hemoglobin $< 10 \text{ g/dl}$.

[Routine follow-up will also include serum electrolytes, creatinine, BUN, LDH, uric acid, AST, ALT, alkaline phosphatase].

Quantitative PCR for the frequency of gene-modified peripheral blood mononuclear cells (PBMC). LAM-PCR, if frequency of gene-modified PBMC $> 1\%$.

If the LAM-PCR results suggest monoclonality, then the following laboratory assessments will be performed, as applicable:

3. Detailed Laboratory Assessment

To determine which cell population may contain an abnormally proliferating clone, immunophenotyping¹ and FACS sorting² will be performed on peripheral blood:

A. Immunophenotyping and determination of absolute numbers of subpopulation:

I. T lymphocytes: Cell surface markers CD3, CD4, CD8, . If the T lymphocyte number is >2 S.D. above normal values for age:

a) If there is evidence of T cell lymphocytosis (CD3), then additional immunophenotypic markers may be done to characterize the stage of differentiation, including: CD1, CD2, CD4+/45RA, CD4+/45RO, TCR α/β , TCR γ/δ ,

b) If there is evidence of TCR α/β , T cell lymphocytosis, then staining for TCR V β usage will be performed, using a broad panel of reagents, e.g., IO Test Beta Mark TM(*Beckman Coulter*).

c) If there is evidence of TCR γ/δ T cell lymphocytosis, then TCR γ and TCR δ usage will be analyzed with a broad spectrum panel.

d) If there is an over-represented TCR family, then PCR for respective TCR monoclonality will be performed.

e) TCR spectratyping may also be used to assess/confirm oligo-monoclonality.

II. B lymphocytes: Cell surface markers CD19 and CD20, Ig κ and Ig λ If there is evidence of abnormal distribution of Ig κ or Ig λ expression, then IgM, IgD, IgG, IgA staining may also be performed to determine if a clonal B cell population is present. If the B lymphocyte number is >2 S.D. above normal values for age:

a) If there is evidence of B cell lymphocytosis (CD19 or CD20), then additional immunophenotypic markers may be done to characterize the stage of differentiation, including: CD10, CD27,

¹ These assays are expected to require 2-5 ml of blood, depending on the WBC count

² These assays are expected to require 5-30 ml of blood, depending on the WBC count

- b) Perform PCR or Southern blot for IgH rearrangement to characterize multiple myeloma, macroglobulinemia and lymphoma, for example.
- c) Perform PCR for EBV (to evaluate for Epstein-Barr infection).
- d) BCR spectratyping may also be used to assess/confirm oligo-monoclonality.

III. NK cells: Cell surface markers CD16, CD56, CD57, CD94, CD158, CD3-negative. If NK or myeloid cells are sustaining the clonal expansion, however, further immunophenotypic assays of the clonality of the hematopoietic lineage are likely to be difficult or impossible, as previous studies have depended on X-inactivation in females or the presence of specific mutations or cytogenetic abnormalities. LAM-PCR integration site analysis of total peripheral blood leukocytes and sorted myeloid cells will be performed to track clonal changes sustained by these cell types. However, marrow analysis may be useful in determining whether hematopoietic differentiation is normal or not. Marrow examination may also be required if there is significant leukocytosis or cytopenia.

B. Sorting (if sufficient cells) for LAM-PCR:

I. Lymphoid cells: Surface markers CD3 for T-cells and, CD19 for B-lymphocytes.

II. Myeloid cells: Surface markers CD33, CD13, and/or CD14.

Genomic material extracted from sorted cells will be used to characterize the site of integration of the gene transfer vector:

Isolation and sequencing of the predominant LAM-PCR fragment.

Identification of the genomic location of integration.

Attempt to study the consequences of the integration event in terms of induction or suppression of gene expression.

III. High resolution cytogenetic analyses of blood and/or marrow cells, as indicated. These analyses can be performed in the presence of any type of leukocyte clonal proliferation and would complement the above studies.

Monitoring for monoclonal expansion or leukoproliferation due to insertional oncogenesis

17.7 Appendix G: Toxicity Table For Grading Severity Of Adverse Experiences (>3 Months Of Age)

17.8 Appendix H: Details of historical HSCT control groups

1. Objective

Historical data from ADA-SCID patients who were treated with Hematopoietic Stem Cell Transplantation (HSCT) at GOSH/UCL (UK) or Duke University Children's Hospital (USA) during the period of 2000-2016 will be collected. HSCT currently corresponds to the standard of care for ADA-SCID patients. These data will be used as historical control groups in a current on-going gene therapy study "*Phase I/II, controlled, open-label, non-randomised, single-centre trial to assess the safety and efficacy of EF1 α S-ADA lentiviral vector mediated gene modification of autologous CD34+ cells from ADA-deficient individuals*". The objective is to compare gene therapy versus HSCT to determine the optimal treatment.

2. Study populations

The control groups will be constituted of patients of 0 to 18 years of age with a confirmed diagnosis of ADA deficiency, transplanted at Great Ormond Street Hospital (UK) or Duke University Children's Hospital (USA) between 2000 and 2016. See inclusion criteria page 64.

3. Data to be collected – GOSH/UCL

GOSH hold a registry / clinical database (European Society for Immunodeficiencies – ESID and European Bone Marrow Transplant Registry - EBMT) displaying information on patients who have received HSCTs. 25 treated patients have been identified between 2000-2016. The patients have given consent for their data to be entered into this registry / clinical database and to be used for other ethically approved studies. ESID and EBMT will allow us to collect the below information:

- Demographics (gender, date of birth, date of death),
- Date of treatment with HSCT
- Method of ADA-SCID diagnosis,
- Previous HSCT including: date, transplant cells, donor type and outcome and whether they needed a second transplant.

However, to make this historical control group valid for marketing authorisation application, our discussions with regulatory agencies suggests that we need to collect further information valuable to compare the efficacy and safety of any new treatment in research vs. current HSCT standard of care as:

- Previous PEG-ADA ERT (and duration of treatment),
- Previous or current immunoglobulin therapy,
- Listing of relevant medical history, including infections (severe or opportunistic infections)
- Vaccination
- Auto-immune disease
- Oncology disease / leukemia
- AEs and SAEs

- Death and reason for death

This information is only available from the patient's records; we therefore plan to re-consent these patients to access their full medical records, and share the information with regulatory agencies and pharmaceutical companies.

4. Data to be collected – Duke University Children's Hospital

Duke University maintain a database of information on patients who have received HSCTs. 10 treated patients have been identified between 2000-2016. The patients have previously given consent to their data being entered into this database and being used for other ethically approved studies.

The following data will be collected from this control group:

- Demographics (gender, year of birth, age at presentation to site),
- Diagnosis (age at and method of ADA-SCID diagnosis),
- HSCT history, including: age at transplant, type of transplant cells and number, donor type and outcome, need for a second transplant, outcome of vaccinations post-transplant,
- Use of PEG-ADA ERT and immunoglobulin therapy (before and after transplant), including time since transplant if reinitiated post HSCT,
- Graft versus host disease,
- Listing of relevant medical history, including infections (severe, recurrent or opportunistic infections) and neurological conditions,
- Previous and Concomitant Treatment,
- Changes in Medical Condition post HSCT, including severe/opportunistic infections, emergent neurological events, autoimmune conditions, oncologic disease, SAEs, bone/skeletal deformities, physical developmental delays or weight loss,
- Lymphocyte subsets (CD3, CD4, CD8, CD19, CD56/CD16 and CD4+/CD45RA cell counts) at baseline and at 1-8 months, 9-16 months and 17-30 months post HSCT,
- ADA activity & ADA metabolites (plasma deoxyadenosine, ADA activity in RBCs, dAXP) at baseline and at 1-8 months, 9-16 months and 17-30 months post HSCT,
- Death and reason for death.

5. Data collection process

This is a retrospective, non-interventional data collection activity; the patients follow routine medical practice. We will contact GOSH patients or their authorised representative and seek their consent to get access to their medical notes and share the information with regulatory agencies and pharmaceutical companies. Teams at GOSH/UCL and Duke University Children's Hospital will work on the collection of data from databases and patients' records, and the data will be entered into an electronic Case Report Form (eCRF). This eCRF will be monitored as per standard process before it can be used for statistical analysis and submission to agencies for review and assessment.

6. Data Analysis

The comparison analysis between gene therapy and HSCT will be done based on the current gene therapy study objective:

Survival and event free survival, defined as need to return to PEG-ADA or second transplant at 1 and 2 years post treatment.

Use of immunoglobulin replacement therapy (IgRT) and severe infections post treatment.

Severe infections, defined as infections requiring hospitalisation or prolonging hospitalization and/or documented infections by opportunistic pathogens (interstitial pneumonia, intractable diarrhoea)

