2.1.3 Treatment Options for ADA-Deficient SCID

2.1.3.1 Allogeneic Bone Marrow Transplantation (BMT)

a. Matched sibling donor BMT

Bone marrow transplantation was first successfully applied in the treatment of a patient with SCID in 1968 ([Gatti, et al, 1968](#)). ADA deficiency was recognized as a cause of SCID in 1972 and patients with ADA-deficient SCID were successfully transplanted at that time ([Giblett, et al, 1972](#); [Parkman, et al, 1975](#)). For SCID patients with an HLA-matched sibling donor, BMT is the treatment of choice. Barring patients with severe pre-existing infections, greater than 90% of SCID patients (with or without ADA deficiency) can be cured with BMT from a matched sibling. Due to the lack of immune reactivity, a matched sibling BMT for SCID is accomplished quite easily; a modest amount of donor bone marrow (e.g. 5×10^7 cells/ kg) is taken directly from the donor and given to the SCID recipient without the use of cytoablation or immune suppression. The majority of patients treated by matched BMT will develop a normal immune system comprised of donor-derived T lymphocytes.

b. Haplo-identical, parental T cell depleted BMT

However, only ~20% of SCID patients will have a matched sibling donor. An alternative treatment which has been developed is the use of haplo-identical (parental) bone marrow, depleted of mature T lymphocytes. The results with T cell-depleted BMT for SCID patients have gradually improved, so that 60-80% of patients will survive with gain of improved-to-normal immune function ([Fischer, et al, 1990](#); [O'Reilly, et al, 1989](#); [Buckley, et al, 1999](#); [Filipovich, 2008](#); [Cowan, 2008](#), [Griffith, 2009](#)). However, despite T cell depletion of the donor marrow, patients can suffer graft versus host disease (GVHD), requiring further immunosuppressive therapy. Some patients will recover only moderate immune function, with B cell deficiency and hypogammaglobulinemia seen in up to half of the patients. Additionally, immune recovery is a slow process, taking 4-12 months, during which time the patients are vulnerable to opportunistic infections.

Buckley and co-workers have reported their results using haplo-identical T-depleted BMT to treat 77 SCID patients, of which 60 of 77 survived (78%). Of the total transplants: 74 of 77 of

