5.1.2 Participant Exclusion Criteria

Exclusion criteria:

1. Age \leq 1.0 months

Appropriate organ function as outlined below must be observed within 60 days of entering this trial.

2. Hematologic

- a. Anemia (hemoglobin < 10.5 g/dl at < 2 years of age, or < 11.5 g/dl at > 2 years of age).
- b. Neutropenia: absolute granulocyte count <500/mm³.
- c. Thrombocytopenia (platelet count < 150,000/mm³, at any age).
- d. INR or PT > 2X the upper limit of normal or PTT > 2.33X the upper limits of normal (patients with a correctable deficiency controlled on medication will not be excluded).
- e. Cytogenetic abnormalities on peripheral blood or bone marrow or amniotic fluid (if available).
- f. Prior allogeneic HSCT with cytoreductive conditioning.

3. Infectious

- a. Evidence of infection with HIV-1, hepatitis B, Hepatitis C, or parvovirus B 19 by DNA PCR within 90 days prior to bone marrow harvest. If other infection is present, it must be under control (e.g. stable or decreasing viral load) at the time of screening.

4. Pulmonary

- a. Resting O₂ saturation by pulse oximetry < 95% on room air.
 - b. Chest x-ray indicating active or progressive pulmonary disease.
5. Cardiac
- a. Abnormal electrocardiogram (EKG) indicating cardiac pathology.
 - b. Uncorrected congenital cardiac malformation with clinical symptomatology.
 - c. Active cardiac disease, including clinical evidence of congestive heart failure, cyanosis, hypotension.
 - d. Poor cardiac function as evidenced by LV ejection fraction < 40% on echocardiogram.
6. Neurologic
- a. Significant neurologic abnormality by examination.
 - b. Uncontrolled seizure disorder.
7. Renal
- a. Renal insufficiency: serum creatinine \geq 1.2 mg/dl, or \geq 3+ proteinuria.
 - b. Abnormal serum sodium, potassium, calcium, magnesium, phosphate at grade III or IV by Division of AIDS Toxicity Scale.
8. Hepatic/GI:
- a. Serum transaminases > 5X the upper limit of normal (ULN).
 - b. Serum bilirubin > 2X ULN.
 - c. Serum glucose > 1.5x ULN.
 - d. Intractable severe diarrhea.
9. Oncologic* (see below)
- a. Evidence of active malignant disease other than dermatofibrosarcoma protuberans (DFSP)
 - b. Evidence of DFSP expected to require anti-neoplastic therapy within the 5 years following the infusion of genetically corrected cells
 - c. Evidence of DFSP expected to be life limiting within the 5 years following the infusion of genetically corrected cells
10. Known sensitivity to Busulfan
11. General

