7.1 Efficacy Population

The primary efficacy population will consist of all patients treated with OTL-101 at UCLA/NIH (current study cohort).

The primary efficacy population from the HSCT historical control cohort will consist of ADA-SCID patients without a medically eligible HLA-matched sibling/family donor and treated with HSCT at either Great Ormond Street Hospital (GOSH) or Duke University from the year 2000 onwards.

Final Version 4.0 Page 11 of 27

Additional efficacy comparisons will be made with:

- ADA-SCID patients with matched related donors treated with HSCT at either GOSH or Duke University from the year 2000 onwards;
- the complete HSCT historical control cohort consisting of ADA-SCID patients with any type of donor treated with HSCT at either GOSH or Duke University from the year 2000 onwards.

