8.3 Efficacy Evaluations

The primary comparison for all efficacy analyses will be between the OTL-101 treated subjects and the allogeneic HSCT controls treated at either GOSH or Duke University without a matched related donor.

Secondary comparisons will be between:

- the OTL-101 treated subjects and the HSCT controls treated at either GOSH or Duke University with a matched related donor;
- the OTL-101 treated subjects and the total group of HSCT controls.

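### The trial's exclusion criteria are not applied to the historical HSCT controls and survival is compared unadjusted, which is likely, though not proven, to favour OTL-101

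*Protocol*

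**What the plan says.** **Controls.** Protocol Appendix H (2. Study populations) states: "The control groups will be constituted of patients of 0 to 18 years of age with a confirmed diagnosis of ADA deficiency". They were transplanted at Great Ormond Street Hospital (GOSH) or Duke "between 2000 and 2016. See inclusion criteria page 64". Protocol 11.5.2 and SAP 7.1 narrow the primary control set to "ADA-SCID patients without a medically eligible HLA-matched sibling/family donor and treated with HSCT" at those two centres from 2000 onwards. Appendix H identifies 25 patients at GOSH and 10 at Duke across all donor types. The number without a matched related donor is not given.

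**OTL-101 subjects.** Protocol 5.1.2 bars age 1.0 month or less, expected survival under 6 months and "Prior allogeneic HSCT with cytoreductive conditioning". On fitness it requires: "Appropriate organ function as outlined below must be observed within 60 days of entering this trial". Four named viruses exclude, and for the rest: "If other infection is present, it must be under control".

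**Comparison.** SAP 8.3 states: "The primary comparison for all efficacy analyses will be between the OTL-101 treated subjects and the allogeneic HSCT controls" without a matched related donor. SAP 8.3.1 uses differences in proportions, Kaplan-Meier curves, the log-rank test and independent Beta(1,1) posteriors. None has covariates, matching or weighting. The sensitivity analyses in SAP 8.3.4 are triggered only by major protocol violations.

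**The concern.** One group was screened for fitness, infection, prior conditioned transplant and short life expectancy. The other was not, as far as the documents show. The clearest mechanism is life expectancy: patients expected to die within 6 months are removed from one group only, and the primary efficacy endpoint is survival at 12 months. Infection is a second plausible route. When Protocol 2.1.3.1 quotes its cure rate for matched-sibling transplant, it sets such patients aside: "Barring patients with severe pre-existing infections, greater than 90% of SCID patients".

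Part of any difference in OS or EvFS may then reflect who was admitted to each group rather than what they received. No planned analysis would show how large that part is.

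**Working it through.** **1. The plan's own figures.** The plan gives no power, effect size or bias figure for the control comparison. Its only design figure (Protocol 11.4) is precision for the 20 OTL-101 subjects alone. The 12% at 19/20 reproduces: exact 95% interval 75.1% to 99.9%, half-width 12.4%. The 7% at 20/20 reproduces only with the whole 5% in the lower tail (86.1% to 100%, half-width 7.0%). The two-sided interval gives 8.4%. Neither figure bears on control selection.

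**2. Eligibility side by side.**

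| Item | OTL-101 | HSCT controls | Checkable from the Appendix H data lists? |
|---|---|---|---|
| Age | over 1.0 month (5.1.2) | 0 to 18 years | Yes: GOSH dates, Duke age at transplant |
| Prior conditioned allogeneic HSCT | excluded | no rule | Prior HSCT yes; conditioning of a prior transplant not listed |
| Infection | four viruses excluded, others controlled | no rule | Listed as history; control at transplant not listed |
| Organ function | limits set | no rule | No laboratory values listed for it |
| Expected survival under 6 months | excluded | no rule | Not listed |
| Donor | no eligible HLA-identical sibling (5.1.1) | no matched sibling or family donor, primary set only | Yes |

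The page-64 pointer does not close the gap. It names inclusion criteria only. If it means Protocol 5.1.1, criterion II there (no HLA-identical sibling donor) cannot govern all controls, because a matched-donor control group is planned. Appendix H also quotes the title of a single-centre trial, whereas SAP 2 describes two centres, so the document being pointed to is itself unclear.

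**3. Size, on assumptions.** Let f be the share of controls who would fail the exclusions, p the 12-month survival of eligible controls and q that of the others. The documents give none of these.

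- Observed control rate = (1 - f)p + fq, so bias = f(p - q).
- With p - q = 30 points: f = 0.10 gives 0.10 x 30 = 3 points; f = 0.30 gives 0.30 x 30 = 9 points.
- Wider range with p = 90%: f = 0.10, q = 50% gives 4 points; f = 0.40, q = 30% gives 24 points.

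**4. Effect on the SAP's Bayesian comparison.** Assume no true difference (OTL-101 and eligible controls both 90%), 20 OTL-101 subjects, and 15, 20, 25 or 35 controls. The SAP states no threshold for the posterior probability that OTL-101 is better, so 0.975 is assumed. For every pair of survivor counts, take the binomial probability and the posterior probability from Beta(1 + X, 1 + N - X) in each group, then add the probabilities of the pairs above 0.975.

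| Bias | Control rate | Chance of apparent superiority, over the four control sizes |
|---|---|---|
| 0 | 90% | 0.7% to 1.9% |
| 3 points | 87% | 2.3% to 4.2% |
| 9 points | 81% | 9.3% to 11.9% |
| 24 points | 66% | 43.1% to 49.1% |

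**5. Could selection explain a whole gap?** Protocol 2.1.3.1 cites OS of 66% (matched unrelated) and 43% (haploidentical). Suppose OTL-101 and eligible controls both had 100% survival. The required f is (100 - observed)/(100 - q).

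- Observed 66%: 34/100 = 34% if all ineligible controls died; 34/60 = 57% if 40% of them survived.
- Observed 43%: 57/100 = 57%, or 57/60 = 95%.

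Such shares are large. Missing exclusions could distort the comparison materially but would not easily account for a gap of that full size.

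**The case against.** The case on the other side has several parts.

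- **Direction.** A reader might infer that the bias always favours OTL-101. The documents do not support that. Protocol 2.1.3.2 says PEG-ADA often went to patients judged too ill for haplo-identical transplant, so transplanted controls may themselves be a fitter selection. Nothing shows worse outcomes for transplant before 1 month of age. This stands: the direction is expected, not demonstrated.
- **Infection.** A reader might infer that the protocol says severe infection determines transplant survival. It only sets those patients aside when quoting a rate for matched-sibling transplant, which is not the primary control group. For other donors it stresses donor match and conditioning. The trial itself admits patients with controlled infection. This also stands.
- **Prior transplant.** Second transplant is an EvFS event timed from transplant (SAP 8.3.1.2), which suggests that the first transplant is normally time zero. That reduces this part of the problem, but no rule says so.
- **Reporting.** Baseline data are presented by cohort: prior HSCT, PEG-ADA and infections (Protocol 11.6.2.2); age, medical history, diagnosis, conditioning and prior enzyme therapy (SAP 8.2.1, 8.2.2, 8.2.3, 8.2.16). Readers would see an imbalance in these items. They would not see what it does to OS or EvFS.
- **Feasibility.** GOSH infection history sits in patient records and needs re-consent (Appendix H). Judging control of infection with the outcome known could add bias. This limits the remedy but does not remove the need for it.

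**Conclusion.** The concern holds in a limited form. The documents apply none of the Protocol 5.1.2 exclusions to the controls, the OS and EvFS comparisons are unadjusted, and no sensitivity analysis addresses comparability. The likely net effect favours OTL-101, chiefly because expected early death is excluded on one side only, but this is not proven.

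The size is unknown. The 3 to 9 points rest on an assumed ineligible share of 10-30% and an assumed 30-point survival gap. They should not be read as an estimate. They are worth noting because the SAP's non-inferiority-like comparison allows 10 points. A reader might also infer that selection could explain the whole advantage over published transplant survival. Step 5 of the working shows that this would need implausibly large or very poorly surviving ineligible shares.

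The change is advisable and cheap. It does not call the primary analysis into question.

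**What to change.** 1. In Appendix H and SAP 7.1, resolve the page-64 pointer and state the control eligibility rules in full.
2. Report how many controls fail each trial exclusion that can be checked, and say which cannot be checked.
3. Add to SAP 8.3.4 a prespecified sensitivity analysis of OS and EvFS at 12 and 24 months, restricted to controls who meet the checkable exclusions:
   - age over 1.0 month at transplant;
   - no prior allogeneic HSCT with cytoreductive conditioning or, where conditioning is not recorded, no prior HSCT, stated as stricter than the trial;
   - no uncontrolled infection at transplant where records allow, judged without knowledge of outcome.
4. Fix these rules before control outcomes are examined. Protocol 2.1.6.2 already reports 100% OS and EvFS in 18 evaluable OTL-101 patients, so later choices would be open to question.

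An age-adjusted penalised model is optional. It does not deal with infection or fitness, and 20 subjects against at most 25 + 10 = 35 controls allow little adjustment.

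**Cost.** Fewer controls and wider intervals in the sensitivity analysis, and some chart review, with re-consent at GOSH. The organ-function exclusions may remain uncheckable. The primary analysis is unchanged.
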